5.1. Number of subjects/centres

Target enrollment for the primary study will be 2400 subjects to obtain approximately 1920 fully evaluable subjects at primary study completion. Target enrollment for extension period will be *a* maximum of 2400 subjects. (All subjects participating in the primary study whose parent(s)/LAR(s) give re-consent for the extension period and who fulfill all *relevant* inclusion/exclusion criteria *may be followed in the extension*.)

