9.3. Determination of sample size

Different RSV-associated LRTI hospitalization rates have been reported in industrialized countries. We observe incidence rates between 16.9 and 44.1 per 1000 children-years in the age group of infants below 6 months of age, between 5.1 and 14.2 per 1000 children-years in the age group of infants between 6-11 months and between 0.4 and 3.7 per 1000 children-years in the age group of children between 12-23 months [Table 12]. These rates are similar to the ones measured in several studies conducted in developing countries [Nair, 2010].

Source	Region	0-5 months	6-11 months	12-23 months
[Hall, 2009]	USA	16.9	5.1	2.7
[Holman, 2004]	USA	41.9	12.8	-
[lwane, 2004]	NY/ Tennessee	18.5	7.4	0.4
[Boyce, 2000]	Tennessee	44.1	15.0	3.7
[Despande, 2003]	UK	36.0	11.3	-
[Vicente, 2003]	Spain	36.8	14.2	-

Table 12RSV-associated LRTI hospitalization rates in industrialized countries
(per 1000 children-years)

USA = United States of America

UK = United Kingdom

Table 13 shows the exact 95% confidence interval (CI) (Poisson exact distribution and normal approximation of the Poisson distribution accounting for a design effect of 4.18) for a range of expected incidence rates of RSV that we can reasonably estimate between 10 and 50 per 1000 children-years in the first year of birth. With an overall sample size of about 320 evaluable subjects by country during the first year of enrollment and with a follow-up period of 1 year after the last subject is recruited, the CI for an expected RSV-associated LRTI hospitalization rate of 20 cases per 1000 children-years is respectively [6.9; 40.8] for the exact Poisson distribution and [0; 51.7] for the normal approximation with design effect of 4.18.

Table 13Precision for expected RSV-associated LRTI hospitalization rate
during the first year of life (per 1000 children-years)

	Number of children-years	Number of cases	RSV-associated LRTI rate (per 1000 children-years)	95% CI Poisson Exact	95% CI Normal approx. with DE			
First year of enrollment (analysis will be performed 1 year after the last subject is recruited)								
Country/region level	320	3	10	[1.9; 27.4]	[0; 32.4]			
	320	6	20	[6.9; 40.8]	[0; 51.7]			
	320	10	30	[13.9; 55.4]	[0; 68.8]			
	320	13	40	[20.5; 67.5]	[0; 84.8]			
	320	16	50	[28.6; 81.2]	[0; 100.1]			
Overall	1280	13	10	[5.1; 16.9]	[0; 21.2]			
	1280	26	20	[13.0; 29.3]	[4.2; 35.8]			
	1280	38	30	[21.0; 40.7]	[10.6; 49.4]			
	1280	51	40	[29.7; 52.4]	[17.6; 62.4]			

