	1280	64	50	[38.5; 63.8]	[25.0; 75.0]			
Second year of enrollment (analysis will be performed 1 year after the last subject is recruited)								
Country/region level	160	2	10	[0.7; 40.1]	[0; 41.7]			
	160	3	20	[3.9; 54.8]	[0; 64.8]			
	160	5	30	[8.4; 68.5]	[0; 84.9]			
	160	6	40	[13.8; 81.6]	[0; 103.4]			
	160	8	50	[21.6; 98.5]	[0; 120.8]			
Overall	640	6	10	[3.4; 20.4]	[0; 25.8]			
	640	13	20	[10.2; 33.7]	[0; 42.4]			
	640	19	30	[17.9; 46.4]	[2.6; 57.4]			
	640	26	40	[25.9; 58.6]	[8.3; 71.7]			
	640	32	50	[34.2; 70.6]	[14.6; 85.4]			

CI = Confidence Interval; RSV = Respiratory Syncytial Virus; LRTI = Lower Respiratory Tract Infection; DE = Design Effect

The design effect measures the increase in the standard error of the estimate due to the sampling design. The following formula will be used to estimate the design effect in the simulation [Bennett, 1991]:

$$DE = \frac{s^2_{cluster \ sample}}{s^2_{simple \ random \ sample}}$$

With

$$s_{cluster \, SAMPLE}^{2} = (c/\sum_{i} x_{i})^{2} (\sum_{i} y_{i}^{2} - 2p \sum_{i} x_{i} y_{i} + p^{2} \sum_{i} x_{i}^{2}) / [c(c-1)]$$

$$s^2_{SIMPLE RANDOM SAMPLE} = p(1-p)/n$$
Where, 'c' is the number of clusters, 'x_i', and 'y_i' are number of children-years and number of cases, respectively in the 'ith' cluster, 'n' is the total number of children-years and 'p' is the overall proportion ' $\sum y_i/\sum x_i$ '.

The intra-cluster correlation ' ρ ' may then be estimated as:

$$\rho = (DE - 1)/[(\sum x_i/c) - 1]$$

Each simulation consists of creating 'c' clusters whose size and incidence vary around a given value. Then the above formula was applied to estimate the design effect in the simulation. Table 14 shows the median result of 1000 simulations (with 5th and 95th percentile). The design effect [Bennett, 1991] can be estimated as following once the intra-cluster correlation value is known or can be assumed:

$$DE = 1 + (b - 1) \rho$$

Where, ρ is the intra-cluster correlation and b is the average number of subjects sampled per cluster. According to the results of simulations, we could assume that the intra-cluster correlation of 0.02 (See Table 14 below) and considering 12 clusters of 160 subjects, we expect that the design effect will take a value of 4.18.

Table 14	Design effect calculated from 1000 simulations and for different
	hypothesis

Hypothesis of the	Results of 1000 simulations				

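### Table 13 applies the full-cohort design effect of 4.18 to overall rows that hold only one enrolment year, so its ten overall clustered intervals are too wide by the protocol's own formula

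*Protocol*

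**What the plan says.** Protocol Section 9.3 gives DE = 1 + (b − 1)ρ, where "b is the average number of subjects sampled per cluster". On the strength of the simulations in Table 14 it says "we could assume that the intra-cluster correlation of 0.02" and continues: "considering 12 clusters of 160 subjects, we expect that the design effect will take a value of 4.18".

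Table 13 then shows two intervals for each assumed rate: an exact Poisson interval, and one from the "normal approximation of the Poisson distribution accounting for a design effect of 4.18". The rows are split by enrolment year. First-year rows have 1280 children-years overall and 320 per country or region; second-year rows have 640 overall and 160 per country or region. The text repeats one country-level result at 20 per 1000, [0; 51.7], described as being "for the normal approximation with design effect of 4.18".

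Section 5.1 gives the cohort size: "Target enrollment for the primary study will be 2400 subjects to obtain approximately 1920 fully evaluable subjects at primary study completion". Appendix C splits recruitment into 1600 in year 1 and 800 in year 2.

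**The concern.** A design effect of this form depends on cluster size. With ρ and the number of clusters fixed, a subset of the cohort has fewer children per cluster and a smaller design effect. One value cannot serve both the 1280 and the 640 rows, and 4.18 fits neither. Table 14 shows the same dependence: with median ρ almost constant (0.021 to 0.022), the median design effect falls from 6.46 to 3.89 as the median cluster falls from 266 to 133 children-years.

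The analyses are descriptive and there is no power calculation, so Table 13 is the plan's only quantitative statement of expected precision. Its clustered column should agree with the formula printed beneath it. As it stands, a reader would conclude that the second-year overall estimate at 20 per 1000 cannot be told apart from zero, which the stated formula does not imply.

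**Working it through.** **Inputs (Protocol Section 9.3 unless noted).** ρ = 0.02; 12 clusters; 160 per cluster; 1280 and 640 children-years in the overall rows; 1920 evaluable (Section 5.1); 95% two-sided, z = 1.96.

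**Where the cohort sizes come from.** 1600 × 0.8 = 1280 and 800 × 0.8 = 640; 1280 + 640 = 1920 = 12 × 160. So 160 per cluster is both enrolment years together. Reading b as children-years per cluster matches the protocol's own expression for ρ, which divides total children-years by the number of clusters.

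**Reproducing the plan.** DE = 1 + (160 − 1) × 0.02 = 4.18. The interval is rate ± 1.96 × √(DE × rate / children-years), with the lower limit cut at 0. Year 1 overall at 20 per 1000: 1.96 × √(4.18 × 0.020 / 1280) = 0.01584, giving [4.2; 35.8] as printed. All 20 design-effect intervals in Table 13 reproduce with 4.18. A binomial variance does not reproduce them: it gives 51.4 where the text has 51.7.

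**Design effect for each overall block.**
- Year 1: b = 1280/12 = 106.7; DE = 1 + 105.7 × 0.02 = 3.11.
- Year 2: b = 640/12 = 53.3; DE = 1 + 52.3 × 0.02 = 2.05.

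**Width ratios before truncation.** √(4.18/3.11) = 1.16; √(4.18/2.05) = 1.43.

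**Overall rows, per 1000 children-years.**

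| Rate | Year 1 printed | Year 1 with DE 3.11 | Year 2 printed | Year 2 with DE 2.05 |
|---|---|---|---|---|
| 10 | [0; 21.2] | [0.3; 19.7] | [0; 25.8] | [0; 21.1] |
| 20 | [4.2; 35.8] | [6.3; 33.7] | [0; 42.4] | [4.3; 35.7] |
| 30 | [10.6; 49.4] | [13.3; 46.7] | [2.6; 57.4] | [10.8; 49.2] |
| 40 | [17.6; 62.4] | [20.7; 59.3] | [8.3; 71.7] | [17.8; 62.2] |
| 50 | [25.0; 75.0] | [28.4; 71.6] | [14.6; 85.4] | [25.2; 74.8] |

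Two lower limits printed as 0 become positive: year 1 at 10 per 1000 (0.3) and year 2 at 20 per 1000 (4.3).

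**The row for which 4.18 is right.** 1920 children at 20 per 1000: 1.96 × √(4.18 × 0.020 / 1920) = 0.01293, giving [7.1; 32.9].

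**Country rows.** These need the clusters per country, so I tried the two readings the document suggests.
- Table 13's own ratio, 1280/320 = 4 countries, gives 12/4 = 3 clusters each. Then b = 106.7 or 53.3, all ten country rows change, and the text's [0; 51.7] becomes [0; 47.3].
- About 400 recruits per country or region out of 2400 gives 6 units and 12/6 = 2 clusters each. Then the 320 rows have b = 160 and DE = 4.18, so they and [0; 51.7] stand. The 160 rows have b = 80 and DE = 1 + 79 × 0.02 = 2.58; at 20 per 1000 this gives [0; 55.2], printed [0; 64.8].

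**The case against.** The strongest reply is that little depends on 4.18. Section 9.3 sets no target width or lower limit, and 2400 is simply 1920/0.8. The design effect is a planning value; for 12 clusters Table 14 gives a 5th to 95th percentile range of 2.57 to 9.49, and 3.11 lies inside it. Protocol Section 9.5.1 says the analysis will derive the design effect from the real data, and SAP Sections 11.1.1 and 11.1.2 use exact Poisson intervals for incidence rates. The discrepancy is also conservative. All of this stands and limits the consequence. It does not make the figures right: a planning value still has to follow the planning formula, and the Table 14 range was simulated at 2400 children-years, not at the yearly subsets.

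A reader might also infer that every clustered interval in the table is wrong. The documents do not support that. The clusters per country are never stated, and on the six-unit reading the five 320 rows are correct as printed. That reading has its own difficulty, because 6 × 320 = 1920 is the whole cohort and not the first enrolment year, but the text does not settle the matter.

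**Conclusion.** The ten overall design-effect intervals in Table 13 contradict the protocol's own formula. They are too wide by a factor of 1.16 in year 1 and 1.43 in year 2 before truncation. This rests on the stated ρ of 0.02 and on the same 12 clusters contributing in both enrolment years.

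The direction matters. It would be easy to read the error as the plan claiming more precision than it has; the reverse is true. It would also be easy to conclude that the sample size is undermined. It is not, because no precision target in the table determines the 2400.

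For the country rows the conclusion is conditional. The second-year rows change on both readings examined; the first-year rows and the quoted [0; 51.7] change on only one of them. The point is a real but modest error in the reported precision, worth correcting because the correction is cheap.

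**What to change.** Recompute the overall rows of the last column of Table 13 with DE 3.11 (first year) and 2.05 (second year). In addition, or as an alternative, add a combined row for 1920 children and use 4.18 for that row only.

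State what a cluster is and how many there are per country or region, then recompute the country rows from that number. Leave the text's [0; 51.7] until this is settled; replacing it now could introduce an error.

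The cost is restated figures in one table, a sentence defining clusters and, depending on that definition, one corrected interval in the text. Enrolment, the exact Poisson column and the planned analyses do not change.

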9.4. Study cohorts/ data sets to be analysed

9.4.1. Screened cohort

The screened cohort will include all subjects screened for the study. All the aggregated information (anonymous) for these subjects will be collected in a logbook.

9.4.2. Analysis Cohorts for the Primary study (first 2 years)

9.4.2.1. Total enrolled cohort at Year 2

The total enrolled cohort will include all subjects enrolled in the *primary* study.

9.4.2.2. Per Protocol Set (PPS) cohort at Year 2

The *PPS* cohort will include all subjects *enrolled in the primary study* meeting all eligibility criteria up to the time of their censoring, either at completion *of epoch 1* or prematurely as drop-out (e.g. withdrawn consent, lost-to-follow-up, lack of compliance). *Additional details are provided in the Statistical Analysis Plan (SAP).*

9.4.2.3. Per Protocol Set (PPS) sub-cohort at Year 2

• The *PPS* sub-cohort *at Year 2* will include subjects *in the PPS cohort at Year 2* for whom a blood sample result will be available (at Month 2, 4, 6, 12, 18 or 24). Analyses will be done on the ATP sub-cohort from the total cohort defined in section 9.4.2 as well as from the ATP cohort defined in section 9.4.2.2.

9.4.3. Analysis Cohorts for the Extension Study

9.4.3.1. Total enrolled cohort for extension

The total enrolled cohort will include all subjects enrolled in the extension study.

9.4.3.2. PPS cohort for extension

The PPS cohort for the Extension study will include all subjects meeting all eligibility criteria up to the time of their censoring, either at study completion or prematurely as drop-out (e.g. withdrawn consent or lost-to-follow-up).

9.5. Derived and transformed data

Data transformations and derived variables will be described in the SAP. However, they may include the following:

- Age of the subject at time of the LRTI case will be expressed in months and will be computed as the difference between the start date of the LRTI case and the date of birth.
- Age of the subject at time of blood sample collection will be expressed in months and will be computed as the difference between the sample collection date and the date of birth.
- Age of the mother at the time of childbirth will be expressed in years and will be computed as the difference between the birth date of the subject and the birth date of the mother.
- Duration of the study for each subject will be computed as the difference between the date of last contact (i.e., active or passive surveillance contact or the date of the censoring) and the date of enrollment (date when ICF was first signed by the subject's parent[s]/LAR[s]).
- All potential LRTI cases identified during the surveillance period will be classified as RTI, LRTI or severe LRTI according to the LRTI case definition and severity scale (refer to Section 4). The cases will also be classified according to the classification of WHO and by Nokes *et al* [Modjarrad, 2016; Nokes, 2004]. First time, the classification will be done at visit level, i.e. according to the data collected at the initial visit and, if applicable, at each additional examination visit. Finally, a classification at case level will be done considering the most severe classification from all visits.

9.5.1. General considerations for statistical analyses

The primary analyses will at least be performed on the **PPS** cohort or sub-cohort. If more than 5% of the subjects are eliminated from the total enrolled cohort, then all analyses **may** also be performed on the total enrolled cohort in addition to the **PPS** cohort or sub-cohort.

When mentioned below in the upcoming analyses sections, analysis by subgroups *may* include:

- Age categories
- Hemisphere/Region/Country
- Birth on-season or off-season
- Collection time of swabs (72 hours/48 hours from the start date of the case (date of the call), 72 hours/48 hours from the reported onset of symptoms).

• For all incidence rate calculations, the 95% CI using the exact Poisson distribution will be estimated, as well the 95% CI using the normal approximation of the Poisson distribution, accounting for a design effect (after having derived the design effect from the real data).

9.6. Analysis of demographics

The distribution of subjects enrolled among the study sites *may* be tabulated overall, by hemisphere, *country, region, center* and/*or* by *other relevant grouping*. The demographic and lifestyle characteristics collected for the enrolled subjects may be summarized overall, by hemisphere, *country, region, center*, and/*or other relevant grouping*.

- Frequency tables will be generated *as appropriate*, for categorical *variables* such as center.
- Mean, median, standard error will be provided *as appropriate*, for continuous data such as age.

9.7. Analysis of Objectives for the Primary Study (birth to 2 years of age):

9.7.1. Co-primary objectives

• To determine the total health burden of RSV-associated RTI with a suspicion of involvement of the lower respiratory tract.

Incidence rates will be calculated as the number of RSV-associated RTI with a suspicion of involvement of the lower respiratory tract over the number of children-years observations, overall and by subgroups.

Descriptive statistics of the different types of healthcare utilization from all healthcare settings will be provided (proportions, duration, etc.) among RSV-associated RTI with a suspicion of involvement of the lower respiratory tract, overall and by subgroups.

• To assess the performance of the LRTI case definition and severity scale for RSV-associated cases.

Incidences rates will be calculated as the number of RSV-associated LRTI/severe LRTI as classified by the LRTI case definition and severity scale and also as classified by the comparator case definitions (WHO and Nokes, et al [Modjarrad, 2016; Nokes, 2004]), over the number of children-years observations, overall and by subgroups.

Descriptive statistics of the different types of healthcare utilization will be provided (proportions, duration, etc.) among RSV-associated LRTI/severe LRTI as classified by the LRTI case definition and severity scale and also as classified by the comparator case definitions (WHO and Nokes, *et al* [Modjarrad, 2016; Nokes, 2004]), overall and by subgroups.

Statistical analysis of agreement will be performed to compare the different case definitions of RSV-associated LRTI/severe LRTI and key healthcare utilization and health outcomes (the hospitalization status, (P) intensive care unit [ICU] attendance, clinical diagnosis of bronchiolitis or pneumonia, death) overall and by age categories.

Table 15 Comparison of two classifications for severe/Non-severe LRTI

RSV-associated cases		Classification of reference (severe/Non-severe)		
		Hospitalized	Not hospitalized	
Alternative classification (severe / Non-severe)	Severe LRTI (LRTI case definition and severity scale)	True positive (TP)	False positive (FP)	
	Non-severe LRTI (LRTI case definition and severity scale)	False negative (FN)	True Negative (TN)	

2x2 contingency tables such as Table 15 will be provided and the following measures of agreement (with 95% CI) will be calculated:

- Sensitivity: TP/ (TP+FN)
- Specificity: TN/ (TN+FP)
- Positive predictive value (PPV): TP/ (TP+FP)
- Negative predictive value (NPV): TN/ (TN+FN)
- Proportion of overall agreement, which is the proportion of cases similarly classified: (TP + TN)/ (TP+FP+FN+TN).
- Cohen's kappa coefficient. The magnitude of the kappa coefficient represents the proportion of agreement greater than that expected by chance.

The same analysis will at least be performed for all the following combinations (reference *vs.* alternative classification):

- Health/healthcare utilization outcome vs. LRTI case definition and severity scale.
- Health/healthcare utilization outcome vs. WHO case definition [Modjarrad, 2016].
- Health/healthcare utilization outcome vs. Nokes, et al case definition [Nokes, 2004].
- WHO case definition [Modjarrad, 2016] vs. LRTI case definition and severity scale.
- Nokes, et al case definition [Nokes, 2004] vs. LRTI case definition and severity scale.

9.7.2. Secondary objectives

• To determine the total health burden of non-RSV-associated RTI with a suspicion of involvement of the lower respiratory tract.

Incidence rates will be calculated as the number of non-RSV-associated RTI with a suspicion of involvement of the lower respiratory tract over the number of children-years observations, overall and by subgroups.

Descriptive statistics of the different types of healthcare utilization will be provided (proportions, duration, etc.) among non-RSV-associated RTI with a suspicion of involvement of the lower respiratory tract, overall and by subgroups.

• To evaluate the association between RSV-associated LRTI, RSV-associated severe LRTI and RSV neutralizing antibodies in the baseline cord blood samples collected from subjects, at birth.

The impact of the level of RSV neutralizing antibodies in the baseline cord blood samples on the risk of having a RSV-associated LRTI and RSV-associated severe LRTI will be assessed through a statistical model.

Incidence rates will be calculated overall and by level of antibodies in the cord blood sample, as the number RSV-associated LRTI/severe LRTI as classified by the case definition and severity scale over the number of children-years observations.

• To determine the prevalence of RSV infection, at 2, 4, 6, 12, 18 and 24 months in a randomly selected sub-cohort of subjects by assessing antibodies in serum.

The primary analysis will be based on ATP sub-cohort for this objective.

Infection by RSV will be assessed (with 95% CI) by time point as the proportion of samples with a positive score of antibody titer after adjusting for baseline antibody results over the total number of samples.

Scores will be determined based on the measured antibody titer *vs*. the expected antibody level at the time of sampling based on the individual baseline (cord blood) value and the average, modelled decay rate.

• To assess the between calendar year variability in the incidence rates of RSVassociated LRTI.

Incidences rates will be calculated as the number of RSV-associated LRTI/severe LRTI as classified by the case definition and severity scale, over the number of children-years observations, in the subgroups of subjects recruited from months 1-6 and from months 13-18.

